**ABBREVIATIONS**

AE	adverse event
CI	confidence interval
CYP	cytochrome P450
DMID	Division of Microbiology and Infectious Diseases
eCRF	electronic case report form
GCP	Good Clinical Practice
IB	Investigator's Brochure
ICF	informed consent form
ICH	International Council for Harmonisation of Technical Requirements for Pharmaceuticals for Human Use
IEC	Independent Ethics Committee
IRB	Institutional Review Board
LD	loading dose
LRTI	lower respiratory tract infection
LTFU	long-term follow-up
MD	maintenance dose
NTP	nucleoside triphosphate
OAT	organic anion transporter
PK	pharmacokinetic(s)
RNA	ribonucleic acid
RSV	respiratory syncytial virus
SAE	serious adverse event
SUSAR	serious unexpected suspected adverse reaction

## 1. INTRODUCTION

Respiratory syncytial virus (RSV) is a ribonucleic acid (RNA) virus and a member of the *Pneumoviridae* family, which also includes human metapneumovirus. The RSV season occurs during winter months in regions with temperate climates in the Northern and Southern hemispheres and throughout the year or peaks semiannually in tropical regions.

RSV causes acute lower respiratory tract infection (LRTI) and is a major cause of hospital admissions and death in young children worldwide. RSV is a leading cause of lower respiratory disease in infants. In 2005, an estimated 33.8 million episodes of RSV LRTI occurred worldwide in infants. Of these, at least 3.4 million severe cases of LRTI required hospitalization, and an estimated 66,000 to 199,000 deaths occurred, mostly in the developing world. In the United States, it has been estimated that annually RSV infection causes 2.1 million emergency room or outpatient visits, including 57,527 hospitalizations. Infants that are born prematurely or close to the RSV season and/or suffering from bronchopulmonary dysplasia or congenital heart disease are at the highest risk of developing severe RSV-related acute LRTI.

RSV infection has been strongly associated with subsequent childhood asthma and wheezing, although the relationship has not been clearly defined. A causal relationship of RSV to subsequent development of asthma is supported by studies showing that the prophylactic use of Synagis® (palivizumab) to prevent RSV infection can decrease the subsequent incidence of recurrent wheezing in high risk infants. In one such study, physician-diagnosed recurrent wheezing was observed in 6.4% and 18.9% of infants in the palivizumab-treated and -untreated groups, respectively ( $p < 0.001$ ). This difference remained significant after adjustment for known risk factors of recurrent wheezing ( $p < 0.001$ ). The American Academy of Pediatrics has however questioned the validity of these findings, describing the reduction of wheezing episodes among recipients of palivizumab as being statistically significant but of clinically minimal significance. A recent study in Native American infants with an efficacious anti-RSV monoclonal antibody (motavizumab), despite reducing RSV admission to hospital by 87%, did not have any impact on medically attended recurrent wheezing.

Asthma appears to be a heterogeneous condition, with signs, symptoms, and clinical evolution that vary according to the patient's disease characteristics or phenotype. Asthma is defined and diagnosed through a combination of clinical symptoms and physiologic abnormalities, generally without reliance upon pathologic or biologic markers. However, the physiologic definition of asthma is relatively nonspecific, consisting of airway hyperreactivity and airflow limitation during expiration, which is variable and/or reversible with bronchodilators. In many asthma patients, the presence of bronchial hyperreactivity is never objectively confirmed.

Three wheezing/asthma phenotypes have been identified: early transient wheezers, non-atopic preschool wheezers, and atopic asthmatics/wheezers. Potential risk factors for each of these classic wheezing/asthma phenotypes presenting in children include prenatal smoking by the subject's mother, subject's exposure to tobacco smoke, wheezing associated with symptoms of acute respiratory infections, whether the subject has siblings or attends kindergarten/day care, personal and/or family history of atopy/allergy, and lung function.

Lumicitabine (also known as JNJ-64041575 or ALS-008176) is a 3',5'-bisisobutyrate prodrug, which is readily metabolized to the cytidine nucleoside analog, JNJ-63549109 (also known as ALS-008112). Once administered, lumicitabine is rapidly and efficiently converted by esterases to JNJ-63549109. Inside cells, JNJ-63549109 is subsequently converted to JNJ-63549109-5'-triphosphate, JNJ-65409136 (also known as ALS-008136), which, as the active metabolite of the compound, is a potent and selective inhibitor of RSV and human metapneumovirus RNA polymerase activity via a classic chain termination mechanism. JNJ-64167896 (also known as ALS-008144), the uridine metabolite of JNJ-63549109, is the inactive major metabolite detected in systemic circulation. [Table 1](#) gives an overview of the investigational product used in this study and its metabolites, including the prior and current compound numbers.

**Table 1: Investigational Product and its Metabolites**

Compound Name/Number	Description
Lumicitabine (JNJ-64041575, ALS-008176)	3',5'-bisisobutyrate prodrug of JNJ-63549109
JNJ-63549109 (ALS-008112)	parent nucleoside, major metabolite of lumicitabine
JNJ-64412309 (ALS-008206)	3'-isobutyrate monoester of JNJ-63549109, minor metabolite
JNJ-64412296 (ALS-008207)	5'-isobutyrate monoester of JNJ-63549109, minor metabolite
JNJ-64167896 (ALS-008144)	uridine metabolite of JNJ-63549109, major metabolite
JNJ-65409136 (ALS-008136)	5'-triphosphate of JNJ-63549109 (NTP), intracellular metabolite, active
JNJ-65409123 (ALS-008137)	5'-monophosphate of JNJ-63549109, intracellular metabolite

Abbreviation: NTP: nucleoside triphosphate.

For the most comprehensive nonclinical and clinical information regarding lumicitabine, refer to the latest version of the Investigator's Brochure (IB).

The term "sponsor" used throughout this document refers to the entities listed in the Contact Information page(s), which will be provided as a separate document.

## 1.1. Background

This study is a long-term follow-up (LTFU) of Study 64041575RSV2004, which evaluates the antiviral activity, clinical outcomes, safety, tolerability, and pharmacokinetics (PK) of orally administered lumicitabine regimens in infants and children aged  $\geq 28$  days to  $\leq 36$  months hospitalized with RSV infection in Study 64041575RSV2004 whose parents/caregivers consented for participation in the LTFU study. This LTFU study, Study 64041575RSV2002, will follow these infants and children for at least 2 years after completion of their treatment course and their final visit of Study 64041575RSV2004 to evaluate the incidence of the clinical diagnosis of asthma and the frequency of wheezing.

A summary of the major findings from nonclinical and clinical studies available at the time of initial protocol writing is presented below. Please refer to the IB for more details.

## Nonclinical Studies

The antiviral activity and selectivity of the parent nucleoside JNJ-63549109 and its prodrug, lumicitabine, were demonstrated in vitro using a combination of cell-based RSV infectious and subgenomic replicon reporter systems, together with cell-extracted replicase and recombinant

RSV polymerase L–P complex. In vivo, lumicitabine was evaluated in the African Green monkey model of RSV infection.

The nonclinical safety profiles for lumicitabine and JNJ-63549109 have been established in multiple in vitro and in vivo studies. In general, lumicitabine was well tolerated in adult rats and dogs for 14 days with no mortality or overt signs of toxicity when administered orally twice daily. In juvenile toxicity studies, doses of 1,000 mg/kg/day caused overt toxicity in both rats and dogs (JNJ-63549109 area under the concentration time curve from time zero to 24 hours postdose of  $\geq 300,000$  and  $\geq 1,375,000$  ng.h/mL in rats and dogs, respectively).

In studies investigating the PK and metabolism profile, the prodrug, lumicitabine, was rapidly and efficiently converted to the parent nucleoside, JNJ-63549109, following both intravenous and oral administration in all species studied. Lumicitabine exhibited high systemic clearance and short half-life. JNJ-64167896, the uridine metabolite of JNJ-63549109, was a major metabolite noted in systemic circulation in monkeys, but not in other species.

Lumicitabine and its major metabolites are predicted to have low potential for cytochrome P450 (CYP)- and transporter-mediated drug-drug interactions, with the possible exception of strong organic anion transporter (OAT) 3 inhibitors.

### **Clinical Studies**

The efficacy of lumicitabine in naturally infected populations has not been demonstrated; however, efficacy has been assessed in healthy adult subjects infected with RSV in a human challenge model (Study ALS-8176-502). In this study, in 62 healthy adult subjects inoculated with RSV and treated with lumicitabine or placebo, data demonstrated that maintenance doses (MDs) of 150 to 500 mg lumicitabine, following a 750 mg loading dose (LD), resulted in rapid, substantial declines in RSV viral load with an accompanying comparable improvement in signs and symptoms of RSV infection compared with placebo-treated subjects.

Data from 6 Phase 1/2a studies (ALS-8176-501, ALS-8176-502, ALS-8176-504, ALS-8176-509, 64041575RSV1001 [ALS-8176-511], and 64041575RSV1003) in healthy adult subjects (N=234), indicate that lumicitabine was well tolerated and that no safety concerns were identified after receiving lumicitabine as single doses up to 3,000 mg or as multiple doses up to 750 mg twice daily on Day 1 followed by up to 500 mg MD (twice daily, every 12 hours) for up to 13 days.

As of 20 April 2017, there have been 2 hematologic serious adverse events (SAEs) of pancytopenia and neutropenia reported in the ongoing clinical studies in hospitalized adult or pediatric subjects with RSV infection, respectively. In addition, there has been 1 non-serious Grade 4 hematologic adverse event (AE) (neutropenia, laboratory Grade 4) in the terminated Study ALS-8176-510 in an adult hospitalized subject with RSV infection. The safety data for all 3 studies have been regularly reviewed by unblinded Independent Data Monitoring Committee, which have identified no potential safety concerns. Factors other than treatment with lumicitabine, including underlying RSV infection, are more likely to have contributed to these serious/severe hematologic AEs. However, a potential contribution of lumicitabine cannot be excluded. The risk-benefit assessment for the continued development of lumicitabine remains

favorable given the population targeted (hospitalized subjects) and the lack of available treatment for RSV infection.

## **1.2. Overall Rationale for the Study**

Given the anticipated effect of lumicitabine treatment on RSV viral kinetics and clinical symptoms (see Section 1), the potential impact on subsequent wheezing and asthma is of interest. This study will therefore evaluate the long-term impact of treatment of RSV infection with lumicitabine on the subsequent development of wheezing or asthma.

## **2. OBJECTIVES, ENDPOINTS, AND HYPOTHESIS**

### **2.1. Objectives and Endpoints**

#### **2.1.1. Objectives**

##### **Primary Objectives**

The primary objectives are to evaluate in infants and children who have been treated with lumicitabine or placebo in Study 64041575RSV2004 during the follow-up period and within 2 years after the RSV infection:

- The incidence of the clinical diagnosis of asthma.
- The frequency of wheezing.

##### **Secondary Objectives**

The secondary objectives are to evaluate during the follow-up period in infants and children who have been treated with lumicitabine or placebo in Study 64041575RSV2004:

- The frequency of wheezing over time.
- The frequency of wheezing episodes over time.
- The long-term safety of lumicitabine.
- The frequency and type of respiratory infections.
- Medical resource utilization.

##### **Exploratory Objectives**

The exploratory objectives are to evaluate during the follow-up period in infants and children who have been treated with lumicitabine or placebo in Study 64041575RSV2004:

- The long-term impact of RSV and its treatment with lumicitabine or placebo on how the subject's health affects normal daily activities for subjects, parents/caregivers, and other family members.
- Impact of the type of wheezing/asthma phenotypes on the frequency of wheezing and clinical diagnosis of asthma.

## **2.1.2. Endpoints**

### **Primary Endpoints**

The primary endpoints are:

- Clinical diagnosis of asthma within the first 2 years after the RSV infection, as diagnosed by a physician and reported by the parent/caregiver.  
All medical information needed to confirm the diagnosis of asthma needs to be collected by the study site personnel.
- Percentage of wheezing days within the first 2 years after the RSV infection, based on information reported by the parent/caregiver.

### **Secondary Endpoints**

The secondary endpoints during the follow-up period are:

- Percentage of wheezing days per month after the RSV infection, based on information reported by the parent/caregiver.
- Number of wheezing episodes after the RSV infection, based on information reported by the parent/caregiver.
- Incidence of reportable AEs and SAEs among subjects, based on information reported by the parent/caregiver and judged by the investigator. Reportable AEs include AEs related to respiratory illnesses and AEs considered at least possibly related to lumicitabine or placebo by the investigator.
- Number and type of respiratory infections among subjects, based on information reported by the parent/caregiver.
- Medical resource utilization including the number of medical visits, emergency room visits, and hospitalizations, all for respiratory conditions only, based on information reported by the parent/caregiver.

### **Exploratory Endpoints**

The exploratory endpoints during the follow-up period are:

- The long-term impact of RSV and its treatment with lumicitabine or placebo on how the subject's health affects the normal daily activities of the subject, the parent/caregiver, and other family members as determined by:
  - The extent to which the subject's daily activities each month were limited by the subject's health.
  - The percentage of days each month that the parent/caregiver missed from work due to the subject's health.
  - The extent to which the parent's/caregiver's productivity while at work was limited by the subject's health.

- The extent to which the subject’s health problems limited the parent’s/caregiver’s ability to engage in normal daily activities.
  - The extent to which the subject’s health problems impacted the parent’s/caregiver’s health.
  - The inability of the parent/caregiver to care for other family members due to the subject’s health.
  - The extent to which the subject’s health limited the parent’s/caregiver’s time spent with other family members.
  - The percentage of days each month that other family members missed from work due to the subject’s health problems.
- Frequency of wheezing and clinical diagnosis of asthma by type of wheezing/asthma phenotype.

Refer to Section 9 for evaluations related to endpoints.

## 2.2. Hypothesis

No formal hypothesis testing will be performed. The hypothesis to be explored is that treatment of RSV-infected infants and children with lumicitabine will decrease the incidence of subsequent asthma and/or wheezing compared with infants and children treated with placebo.

## 3. STUDY DESIGN AND RATIONALE

### 3.1. Overview of Study Design

This is a global multicenter, blinded, LTFU study to evaluate the incidence of the clinical diagnosis of asthma and the frequency of wheezing in infants and children (otherwise healthy or with underlying comorbidities for severe RSV) who have completed their treatment course and their last planned study-related visit in a previous Phase 2 study, 64041575RSV2004, in which they received lumicitabine or placebo for the treatment of RSV infection. Subjects will be followed for at least 2 years following treatment. Participation in this LTFU study is optional for study sites. This LTFU study will be offered to subjects of Study 64041575RSV2004 if their site decides to participate in the LTFU.

No study drug will be administered in this study. Subjects may be enrolled within 3 months after randomization in Study 64041575RSV2004. Assessments will be performed at the time points specified in the [Time and Events Schedule](#). The last visit of Study 64041575RSV2004 (ie, Day 28) may be combined with the entry visit of this LTFU study.

Parents/caregivers will be provided with a wheezing parent/caregiver card and a medication parent/caregiver card, both of which should be completed on a daily basis. These parent/caregiver cards will serve as reminder cards when a study site responsible person interviews the subject’s parent/caregiver in order to complete a standardized paper questionnaire. The questionnaire will be completed by a study site responsible person at each study site visit as noted in the [Time and Events Schedule](#) and during a monthly telephone call (calendar month  $\pm 7$  days) between study site visits (see Section 9.1.3).

An unblinded interim analysis will be performed when all subjects from the first season in Study 64041575RSV2004 who are enrolled in this LTFU study complete the 18 months follow-up assessment of this LTFU study. Sites and the parents/caregivers of subjects will remain blinded. This interim analysis will serve to evaluate the need for an extension of the follow-up period (see Section 11.6).

The planned total study duration for each subject will be 24 months unless the decision is taken to extend the duration of follow-up in this study, based on the interim analysis.

### **3.2. Study Design Rationale**

This study is a LTFU study in subjects who received lumicitabine or placebo in Study 64041575RSV2004.

## **4. SUBJECT POPULATION**

The inclusion and exclusion criteria for enrolling subjects in this study are described in the following 2 subsections. If there is a question about the inclusion or exclusion criteria below, the investigator must consult with the appropriate sponsor representative and resolve any issues before enrolling a subject in the study. Waivers are not allowed.

### **4.1. Inclusion Criteria**

Each potential subject must satisfy all of the following criteria to be enrolled in the study:

1. Male or female infants and children who were previously randomized in Study 64041575RSV2004 for the treatment of RSV infection and who completed the planned course of the study drug and the last study-related visit of Study 64041575RSV2004.
2. The subject's legally acceptable representative must sign an informed consent form (ICF) indicating that he or she understands the purpose of, and procedures required for, the study and is willing for the subject to participate in the study.

## **4.2. Exclusion Criteria**

Any potential subject who meets any of the following criteria will be excluded from participating in the study:

1. The subject's legally acceptable representative, ie, parent/legal guardian/caregiver, is not able to maintain reliable communication with the investigator.
2. Any condition for which, in the opinion of the investigator, participation would not be in the best interest of the subject (eg, compromise the well-being) or that could prevent, limit, or confound the protocol-specified assessments.

## **5. TREATMENT ALLOCATION AND BLINDING**

The parent/caregiver of subjects who enroll in this study and their investigators will remain blinded to the study treatment (lumicitabine or placebo) administered in the previous Study 64041575RSV2004 until the completion of this LTFU study, including any extension period.

## **6. DOSAGE AND ADMINISTRATION**

Not applicable as no study drug will be administered in this study.

## **7. TREATMENT COMPLIANCE**

Not applicable as no study drug will be administered in this study.

## **8. MEDICATIONS**

There are no medication restrictions in this study.

Medication use will be monitored throughout the study from signing of the ICF until the last study-related activity. Parents/caregivers will be required to bring all medications to the study site visit. Additionally, parents/caregivers will be required to document on a daily basis use of medication on a medication parent/caregiver card (see [Attachment 4](#)), which will serve as a reminder card to be used during the study site visits and monthly phone calls between study site visits for recording the medication used for respiratory infections and illnesses on the Concomitant Medication page of the electronic case report form (eCRF) by the study site personnel.

Parents/caregivers will be required to return the completed parent/caregiver cards to the study sites every 3 months (eg, in person or by mail/email/fax when no study site visit is scheduled).

## 9. STUDY EVALUATIONS

### 9.1. Study Procedures

#### 9.1.1. Overview

The [Time and Events Schedule](#) summarizes the frequency and timing of clinical and safety assessments.

No blood sampling will be performed in this study.

#### 9.1.2. Entry Visit

Screening can be performed as soon as it is confirmed that the subject participated in Study 64041575RSV2004 and completed the planned course of the study drug and the last study-related visit. Subjects may be enrolled within 3 months after randomization in Study 64041575RSV2004. The last visit of Study 64041575RSV2004 (ie, Day 28) may be combined with the entry visit of this LTFU study (Study 64041575RSV2002).

At the entry visit, after signing the ICF, the overall eligibility of the subject to participate in the study will be assessed.

Baseline demographics and medical/family history from the previous Phase 2 Study 64041575RSV2004 will be captured in the LTFU (Study 64041575RSV2002) eCRF. Medical and family history to identify risk factors for wheezing/asthma at baseline, including prenatal smoking by the subject's mother, subject's exposure to tobacco smoke, wheezing associated with symptoms of acute respiratory infections, whether the subject has siblings or attends kindergarten/day care, and personal and/or family history of atopy/allergy will be recorded in the eCRF.

Parents/caregivers will be provided with the medication and wheezing parent/caregiver cards, both of which need to be completed on a daily basis (see [Attachment 3](#) and [Attachment 4](#)).

During the entry visit, a clinical questionnaire (see [Attachment 2](#)) needs to be completed by a study site responsible person, by interviewing the subject's parent/caregiver, to collect the following information:

- Wheezing.
- Diagnosis of asthma, eczema, and allergic rhinitis. All medical information needed to confirm the diagnosis of asthma, eczema, and allergic rhinitis needs to be collected by the study site personnel.
- Impact of the subject's health status on normal daily activities for subjects, parents/caregivers, and other family members.

This questionnaire will capture information since the last study visit:

- If the entry visit of Study 64041575RSV2002 coincides with the last visit of Study 64041575RSV2004 (ie, Day 28), the "last study visit" in the questionnaire refers to

the Day 14 visit in Study 64041575RSV2004. Any recalled events in the questionnaire will be related to this time period.

- If the entry visit of Study 64041575RSV2002 takes place after the last visit of Study 64041575RSV2004 (ie, Day 28), the “last study visit” in the questionnaire refers to the Day 28 visit in Study 64041575RSV2004. Any recalled events in the questionnaire will be in the last 30 days or less (if the entry visit to last study visit of Study 64041575RSV2004 is less than 30 days).

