2.5. Study Day and Relative Day

The reference day is the date of informed consent in study 64041575RSV2002. All assessments will be assigned a day relative to this day.

The relative day for a visit is defined as:

$$\text{Visit day} - (\text{informed consent in study 64041575RSV2002}) + 1$$

For the monthly reports, the visit schedule will be based on the entry dates of each monthly report; the entry of the first report is the Screening visit, and each subsequent entry is considered as the next Monthly report (starting with Month 2, reflecting the time since the RSV event).

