5. EFFICACY

5.1. Primary Efficacy Endpoint(s)

5.1.1. Definition

The primary endpoints are:

1. Clinical diagnosis of asthma within the first 2 years after the RSV infection, as diagnosed by a physician and reported by the parent/caregiver. This will be derived based on the completed study questionnaires at each visit/telephone call until the final visit. It is either “Yes” or “No”.
2. The percentage of wheezing days in a subject within the first 2 years after the RSV infection will be calculated as:

$$\text{Percentage of wheezing days} = \left(\frac{\text{number of wheezing days}}{\text{day of study completion} - \text{day of informed consent} + 1} \right) * 100$$

The percentage will be rounded to the nearest integer. Number of wheezing days is the sum of all days that were reported in the Monthly visit reports. The day of informed consent is the informed consent of the RSV2002 study.

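### As most naturally read, the SAP counts wheezing days recalled from before consent in the numerator of the primary wheezing percentage, while the denominator starts at consent

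*Protocol*

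**What the plan says.** Protocol 9.1.2 makes the entry questionnaire retrospective: "This questionnaire will capture information since the last study visit". Two cases follow. If entry coincides with the last parent-study visit (Day 28), the reference visit is "the Day 14 visit in Study 64041575RSV2004. Any recalled events in the questionnaire will be related to this time period". If entry is later, the reference is the Day 28 visit and "Any recalled events in the questionnaire will be in the last 30 days or less". Entry timing varies: "Subjects may be enrolled within 3 months after randomization in Study 64041575RSV2004". Consent belongs to the same visit: "At the entry visit, after signing the ICF, the overall eligibility of the subject to participate in the study will be assessed". The daily wheezing cards are first handed out at entry.

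In SAP 2.5, on the monthly reports, "the entry of the first report is the Screening visit, and each subsequent entry is considered as the next Monthly report". SAP 5.1.1 defines the numerator of the primary percentage: "Number of wheezing days is the sum of all days that were reported in the Monthly visit reports". The denominator is the day of completion minus the day of consent to this follow-up study, plus 1. SAP 5.1.1 puts no date limit on the wheezing days. The endpoint is named for the two years following the RSV infection, not following consent.

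**The concern.** A percentage of days should count events only on days that are also in its denominator. Here the entry report can contribute days before consent, and the denominator cannot contain them. This happens even with complete data, so it is separate from any missing-data question.

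The number of such days is set by visit scheduling, not by the child's wheezing. Two children with the same history can therefore receive different values of a primary endpoint. These days were also recalled without this study's daily card, unlike the days that follow. The formula has no ceiling at 100%.

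**Working it through.** The plan gives no wheezing rate or expected percentage, so there is no stated figure to reproduce. The check evaluates the SAP formula directly.

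**Inputs**
- Consent day = entry day (Protocol 9.1.2 and the Time and Events Schedule).
- Look-back L = 14 days for entry at Day 28 (13 if the Day 14 date itself is left out); L = min(30, entry day − 28) for later entry.
- Entry runs from Day 28 to about Day 91, taking 3 months as 91 days.
- Follow-up of 24 months, taken as 730 days, so the denominator is 730 + 1 = 731. The ±7-day visit window gives 724 to 738.
- Wheezing rates are assumptions, because the documents give none.

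**Look-back by entry day**

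| Entry day | L (days) | Days since Day 28 never captured |
|---|---|---|
| 28 | 14 | 0 |
| 29 | 1 | 0 |
| 35 | 7 | 0 |
| 42 | 14 | 0 |
| 58 | 30 | 0 |
| 75 | 30 | 17 |
| 91 | 30 | 33 |

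The number of possible extra days falls from 14 to 1 between Day 28 and Day 29, then climbs to 30.

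**Upper bound of the excess** = 100 × L / denominator, with wheezing on every look-back day

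| Follow-up | Denominator | L = 14 | L = 30 |
|---|---|---|---|
| 24 months | 731 | 1.92 points | 4.10 points |
| 12 months | 366 | 3.83 points | 8.20 points |
| 6 months | 183 | 7.65 points | 16.39 points |

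The ±7-day window moves the 24-month figures only to 1.90–1.93 and 4.07–4.14. If half the look-back days have wheezing, the 24-month excess is 7/731 = 0.96 or 15/731 = 2.05 points.

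**Worked case:** 5% of days with wheezing after consent, 50% in the look-back. Post-consent wheezing days = 0.05 × 731 = 36.55.
- L = 14: SAP formula (36.55 + 7)/731 = 5.96%; days from consent only, 5.00%; denominator extended to match, 43.55/745 = 5.85%.
- L = 30: SAP formula (36.55 + 15)/731 = 7.05%; days from consent only, 5.00%; denominator extended to match, 51.55/761 = 6.77%.

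Across assumed rates of 2%, 5% and 10% after consent, and the same rate, 25%, 50% or 100% in the look-back, extending the denominator changes the value by only 0.04 to 0.56 points.

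**Values above 100%**
- Wheezing every day over full follow-up: (731 + 14)/731 = 101.9%, or (731 + 30)/731 = 104.1%.
- Last contact 10 days after consent, taken as the completion day, with 14 pre-consent wheezing days and none afterwards: denominator 10 + 1 = 11, and 14/11 = 127%.

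**The case against.** The strongest reply is that inclusion is inferred. SAP 5.1.1 refers to the monthly reports; SAP 2.5 calls the first entry Screening and starts the month numbering at Month 2; SAP Table 3 separates Screening from the months. The only analysis phase (SAP 2.1) opens at the start of the consent date, and the 2-year episode count in Table 2 is bounded at consent. This stands so far as the SAP never says outright that pre-consent days count. It does not remove the problem. SAP 2.5 places the Screening entry at the head of the monthly series, SAP 2.1 assigns assessments by database visit rather than by the date of the wheezing day, and the entry report is completed within the phase. Section 5.1.1 has no bound like the one in Table 2.

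A reader might infer that wheeze from the acute infection inflates the endpoint. The documents do not support that. They give no duration for index-illness wheeze. It is plausible for Days 14 to 28, but later entrants recall only time after Day 28; at Day 91 entry that is about Days 61 to 90.

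A reader might also infer that every affected child's value is too high overall. Look-back wheeze can only raise it, but SAP 2.1 does not impute missing visits, so unreported days stay in the denominator and pull the other way.

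Finally, the look-back days lie inside the named two-year window, so removing them is not the only coherent remedy. And the listings in SAP 5.2.2 would make the affected days visible. Both points are fair, but neither settles which days the primary ratio covers.

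**Conclusion.** The point holds as a mismatch on the most natural reading of SAP 2.5 and 5.1.1; at the least, a primary endpoint is open to two readings. With 24 months of follow-up the excess is at most 1.9 points (14-day look-back) or 4.1 points (30-day look-back), and about half that if half the look-back days have wheezing. It grows as follow-up shortens, and the result is not bounded at 100%. These figures assume that consent is signed on the day of entry and that the Screening report is counted.

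The practical reach is limited. SAP 2.4 states that only 7 subjects were included, and no hypothesis is tested. The effect is on descriptive summaries and on comparability between children. It should be corrected, but it does not undermine an inference the plan intends to draw.

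**What to change.** State in SAP 5.1.1 which days count, and make numerator and denominator cover the same days.

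- **Preferred:** count a wheezing day only if its calendar date is on or after the date of consent to this follow-up study, so that the percentage rests on days supported by the daily card. Apply the same limit when summing episodes across months in SAP Table 2, so that the sum agrees with the consent bound already stated there. List the recalled pre-consent days separately.
- **Alternative:** keep those days and start the denominator at the first day covered by the entry report. This retains days inside the named two-year window, but mixes recalled and card-supported days.

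The preferred option costs one sentence in 5.1.1, a matching clause in Table 2 and a date filter. The calendar in Section A of the questionnaire already records individual days. Its small downside is that recalled in-window days leave the primary percentage. It also does not make early and late entrants fully comparable: for a child entering at Day 28, Days 28 to 79 count, and for one entering at Day 80 they do not. The report should note that remaining difference in the start of observation.
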